12.2 Serious Adverse Events (SAEs) and Serious Adverse Drug Reactions (SADRs)

Definition Serious Adverse Event (SAE)/Serious Adverse Drug Reaction (SADR)

Any untoward medical occurrence that at any dose:

- Results in death
- Is life-threatening (an event in which the subject was at risk of death at the time of the event; it does not refer to an event which hypothetically might have caused death if it were more severe)

- Requires inpatient hospitalization or prolongation of an existing hospitalization
- Results in persistent or significant disability/incapacity
- Is a congenital anomaly/birth defect

In addition, medical and scientific judgment should be exercised in deciding whether other conditions should also be considered serious, such as important medical events that may not be immediately life-threatening or result in death or hospitalization, but may jeopardize the subject or may require intervention to prevent one of the other outcomes listed above. These should also be considered serious.

Examples of such events are intensive treatment in an emergency room or at home for allergic bronchospasm; blood dyscrasias or convulsions that do not result in hospitalization; or development of drug dependency or drug abuse.

During the course of the study:

If not associated with significant worsening of PD symptoms, a hospitalization for dose adjustments of LCIG will not be regarded as an SAE. A hospitalization because of a Product Quality Complaint such as a device dislocation without AE (i.e., without health impairment) will not be regarded as an SAE.

All SAEs that are spontaneously reported within 30 days of a subject's last visit are to be collected and reported as previously described.

12.2.2 Reporting of Serious Adverse Drug Reactions and Suspected Unexpected Serious Adverse Drug Reactions to Regulatory Authorities and Investigators

All serious adverse drug reactions will be subject to expedited reporting per local requirements and regulations. All suspected unexpected serious adverse drug reactions (SUSARs) will be subject to expedited reporting and any additional local requirements and regulations. Additionally, post-study SUSARs that occur after the subject has completed a clinical study and are reported by the Investigator to the Sponsor (or an authorized representative) qualify for expedited reporting. Expeditedness is assessed according to the Investigator's Brochure (IB) for LCIG.¹⁴

The Sponsor (or an authorized representative) is responsible for submitting reports of SUSARs to the appropriate national regulatory authorities within the required reporting period. All Investigators participating in ongoing clinical studies with the therapeutic system will be notified by the Sponsor (or an authorized representative) of all SUSARs that require prompt submission to the IEC/IRB. The Sponsor (or an authorized representative) or the Investigator (according to national provisions) is responsible for notifying the IECs/IRBs in writing of the SUSARs within the required reporting timelines. Copies of the notification will be maintained by both the Investigator and the Sponsor (or an authorized representative) in the study documentation files.

12.3 Pregnancies

If a subject should become pregnant during the study, the event will be reported on a Pregnancy form within 1 working day of the study site's knowledge of the pregnancy. The Pregnancy form is to be faxed to the Sponsor (or an authorized representative) at the contact numbers listed in Section 12.2.1.

The pregnancy evolution and outcome (i.e., the health status of the newborn), is to be reported on a Pregnancy Outcome form and reported to either the Sponsor (or an authorized representative) within 1 working day of the study site's knowledge of the event.

13.0 Statistical Methods and Determination of Sample Size

Data handling will be the responsibility of Quintiles, Inc. The data will be inspected for inconsistencies by performing validation checks. Any inconsistencies found will be resolved by the monitor after contacting the Investigator. When the data in the database are considered clean and the subjects allocated to subject samples in a data review, the database will be locked to prevent unauthorized access. Next, the database will be made available as SAS[®] files for statistical analysis.

All details regarding the statistical analysis and the preparation of tables, listings and figures will be described in the Statistical Analysis Plan prepared by Quintiles, Inc. and approved by the Sponsor before database lock.

The statistical analysis will be performed by Quintiles, Inc.

13.1 Statistical Objective

The primary statistical objective of this study will be to evaluate the long-term safety of LCIG.

13.2 Analysis Populations

Definitions of analysis populations:

1. Safety Population:
The Safety Population includes all subjects who have taken at least one dose of study medication in this study. The Safety Population will be used for all analyses unless noted otherwise.
2. Efficacy Population:
The Efficacy Population includes all subjects who have taken at least one dose of study medication in this study and have at least one efficacy assessment in this study.

This is an open-label study with a single, active treatment group; all subjects in this study will receive LCIG.

13.3 Statistical Methods

Safety Analysis

The Safety Population will be used for the analysis of the safety and tolerability data.

Adverse events will be coded using the Medical Dictionary for Regulatory Activities (MedDRA). A treatment-emergent adverse event (TEAE) is defined as any adverse event that begins or worsens in severity on or after the first dose of study drug in the current study and within 30 days of the end of LCIG treatment in the current study. For subjects transferring to commercial product, the end of treatment in the current study will be the last dose of study drug. For subjects who are discontinuing LCIG treatment, the end of treatment in the current study will be the removal of the PEG-J tube. The following summaries of TEAE's will be prepared:

- Incidence of treatment-emergent adverse events
- Incidence of treatment-emergent serious adverse events

- Incidence of treatment-emergent adverse events resulting in study termination
- Incidence of treatment-emergent adverse events of special interest

The following additional analyses of safety will also be prepared:

- Summary of vital sign and weight values and mean change from Baseline over time
- Incidence of potentially clinically significant vital sign and weight values
- Summary of clinical lab values and mean change from Baseline to Endpoint
- Summary of special lab values and mean change from Baseline over time
- Incidence of potentially clinically significant clinical lab values
- Summary of MIDI at Baseline and during treatment
- Summary of C-SSRS
- Incidence of device complications

Efficacy Analysis

The Efficacy Population will be used for analyses of efficacy. The mean change from baseline to endpoint will be summarized for the following efficacy endpoints.

- "Off" time as measured by the Parkinson's Disease Diary
- "On" time without troublesome dyskinesia (sum of "On" time without dyskinesia and "On" time with non-troublesome dyskinesia) as measured by the Parkinson's Disease Diary
- UPDRS total score, Parts I, II, III and IV scores, and dyskinesia item score
- PDQ-39 summary index and domain scores

For the analysis of change from baseline in efficacy measures, each subject's baseline will be their baseline measure in the first LCIG study in which they participated (e.g., Study S187.3.001, S187.3.002 or S187.3.004).

Additional Analysis

Subject disposition will be summarized including the primary reason for premature discontinuations and a listing of all subjects not included in the safety population.

Descriptive statistics will be provided for demographics and baseline characteristics.

Concomitant medication use will be summarized over time.

Baseline and Endpoint

Unless noted otherwise, the baseline value for a variable is defined as the last non-missing value collected in the current study or the previous open-label LCIG study before the first dose of study drug in the current study.

The endpoint value for a variable is defined as the last non-missing value assigned to the treatment period in the current study for the subject. For subjects transferring to commercial product, the end of treatment in the current study will be the last dose of study drug. For subjects who are discontinuing LCIG treatment, the end of treatment in the current study will be the removal of the PEG-J tube.

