11.0 Study Assessments (Criteria for Evaluation) and Flow Chart

Final assessments from the previous open-label LCIG study will serve as the baseline assessments for this study. All assessments must take place within a window of ± 14 days from the scheduled visit day unless otherwise noted.

In the event a study subject transfers to LCIG commercial product, all assessments under termination assessments in the Flow Chart of Assessments must be completed prior to transferring to commercial product, with the exception of the removal of the PEG tube which will remain in place.

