LCIG is administered as part of a therapeutic system that includes devices and implantation procedures. Subjects who discontinue LCIG therapy are to have their PEG-J removed.

For subjects who have prematurely discontinued or completed the study, and have reported a final PEG-J removal on the DI raw data panel that is after their last day of study drug administration and before the Cutoff Date (interim analysis only), their date of last 3005 PEG-J exposure will be the date of PEG-J removal. For all other subjects who have prematurely discontinued or completed the study, their date of last 3005 PEG-J exposure will be the earlier of 1) the date of discontinuation or study completion collected on the DS raw data panel, and 2) the Cutoff Date (interim analysis only).

For the 2015 interim analysis, the date of the last 3005 PEG-J exposure for all ongoing subjects will be the Cutoff Date.

The date of the last 3005 PEG-J exposure is the key variable RFENDT2N.

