8.1.5 Subject Enrollment and Disposition

As previously described, Study 3005 is an extension study. Subjects will be assigned to an enrollment cohort based on the study in which they received their first LCIG infusion. Due to the similarity in study design, Study 3001 and Study 3002 will be considered a single enrollment cohort. The number and percentage of subjects in each of the following enrollment cohorts will be summarized:

- Subjects who received their first LCIG infusion in Study S187.3.001 or Study S187.3.002
- Subjects who received their first LCIG infusion in Study S187.3.003
- Subjects who received their first LCIG infusion in Study S187.3.004

Subjects are expected to continue in the study until commercial LCIG becomes available to them. If commercial LCIG becomes available to a subject, a final visit shall be scheduled and the subject will be regarded as having completed the study if they complete this final visit. If at any time after providing informed consent, a subject prematurely discontinues their participation in the study, the primary reason for premature discontinuation shall be recorded on the "Study Termination" CRF. The primary reason can include one of the following:

- Adverse Event
- Lack of Efficacy
- Lost to Follow-up
- Withdrew Consent
- Administrative
- Protocol Violation

Premature discontinuations will be summarized by 3005 treatment year after allocating each premature discontinuation to a 3005 treatment year based on the study day of the subject's last dose date and the study day intervals described in Section 6.4.9.

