For a missing/incomplete stop date the maximum of the following will be imputed:

- The minimum of the latest possible stop date and the date of last administration of investigational study drug
- The earliest possible stop date
- The earliest possible start date

Here, the earliest (latest) possible date is defined as:

- The date itself if it is possible
- The date of the first (last) day of the month, if month and year are available but the day is missing
- The date of the first (last) day of the year, if year is available but day and month are missing
- A very early (late) date, for example, 01JAN1000 (01JAN3000), if the date is completely missing

From this data the following will be determined and used for presentation in the applicable tables and listings:

- Treatment-Emergent Adverse Events (TEAEs): Defined as AEs which started on or after the Date of the First 3005 LCIG Infusion and within 30 days of the Date of the Last 3005 PEG-J Exposure.
- Treatment-Emergent Serious Adverse Events (TESAEs): Defined as TEAEs regarded by the Investigator as Serious.
- TEAEs that are at least possibly related to the therapeutic system: Defined as TEAEs assessed as having a "Possible" or "Probable" relationship to the investigational therapeutic system and includes those events where the relationship is missing.
- Severe TEAEs: Defined as TEAEs assessed as being "Severe" in intensity and includes those events where the severity is missing.
- TEAEs that led to premature discontinuation: Selected as those events where: "Led to Study Termination" is indicated as "Yes."
- TEAEs with fatal outcome as reported on the "Adverse events" CRF.
- TEAEs in the following categories have been defined as TEAEs of special interest:
 - Procedure and device associated events
 - Polyneuropathy (broad search as well as narrow search)
 - Weight loss

- Cardiovascular fatalities
- Respiratory tract aspiration including aspiration pneumonia/pneumonitis

TEAEs are included in a category of special interest based on their PT and, in the case of cardiovascular fatalities, their outcome. The list of PT's assigned to each category is included as Appendix 12.4. Only TEAEs where an outcome of "Fatal" has been reported on the "Adverse Event" CRF are to be included in the category of cardiovascular fatalities. All events with PT's other than those assigned to the procedure and device associated AESI category will be included in summaries of events that are not procedure and device related.

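### For subjects who complete by moving to commercial LCIG, the SAP closes the adverse-event window 30 days after the study completion date, not 30 days after the last study dose as the protocol says, and does not declare the change

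*Protocol*

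**What the plan says.** **Protocol.** Section 13.3 counts an adverse event as treatment-emergent if it starts or worsens from the first study dose up to a point "within 30 days of the end of LCIG treatment in the current study". It then defines that end in two ways. For one group: "For subjects transferring to commercial product, the end of treatment in the current study will be the last dose of study drug". For the other: "For subjects who are discontinuing LCIG treatment, the end of treatment in the current study will be the removal of the PEG-J tube". The Baseline and Endpoint paragraph of the same section repeats both rules for endpoint values. Section 11.0 says that the termination assessments "must be completed prior to transferring to commercial product", "with the exception of the removal of the PEG tube which will remain in place".

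**SAP.** Section 8.1.5 treats transfer as the expected way to finish: "the subject will be regarded as having completed the study if they complete this final visit". Section 6.4.1 defines the last PEG-J exposure date (RFENDT2N). If a final PEG-J removal after the last dose is recorded, that removal date is used. For everyone else who has completed or discontinued, "their date of last 3005 PEG-J exposure will be the earlier of 1) the date of discontinuation or study completion" as held on the DS panel, and the Cutoff Date at the interim. Section 8.5.1 counts TEAEs that start "within 30 days of the Date of the Last 3005 PEG-J Exposure". Section 6.4.6 uses the same anchor for all safety data, adding 30 days for adverse events and 1 day for everything else. Section 10.1 lists two departures from the protocol: the efficacy baseline and the merged categories of events of special interest. The end of the safety window is not among them.

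**The concern.** The protocol separates subjects who stop LCIG from subjects who move to the marketed product. Appendix B shows that the two-part rule came in with this amendment, and SAP 4.0 says that the SAP covers Amendment 4. The SAP carries over only the tube-removal part. A transferring subject keeps the tube, so normally has no removal date, and falls under the completion-date rule.

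Long-term safety is the primary statistical objective (Protocol 13.1), TEAE incidence is the first safety summary listed in Protocol 13.3, and transfer is the planned exit. The substituted date therefore applies to completers in general. A reader of the study report would assume that the protocol's TEAE definition had been used, because nothing says otherwise. The SAP also builds Treatment Period End Day on this date, and that day sets the denominators of the by-year adverse-event tables (SAP 8.5.1).

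**Working it through.** The plan gives no figure to reproduce; the check is date arithmetic.

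**Inputs**
- L: day of the last study dose. It is collected on the DS panel and used for the last-infusion date, RFENDTN (SAP 6.4.1).
- C: day of study completion, also on the DS panel (SAP 6.4.1).
- 30 days: the adverse-event window after the end of treatment, the same length in both documents.
- C − L: not stated anywhere. The values below, −14 to +14 days, are assumptions for illustration.

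**Window end for a transferring subject with no later PEG-J removal (final analysis, no cutoff)**
- Protocol 13.3: L + 30
- SAP 6.4.1 and 8.5.1: RFENDT2N + 30 = C + 30
- Difference: (C + 30) − (L + 30) = C − L

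| Assumed C − L (days) | Protocol window closes | SAP window closes | Effect |
|---|---|---|---|
| −14 | L + 30 | L + 16 | last 14 days of the protocol window lost |
| −7 | L + 30 | L + 23 | last 7 days lost |
| 0 | L + 30 | L + 30 | none |
| +7 | L + 30 | L + 37 | 7 days added |
| +14 | L + 30 | L + 44 | 14 days added |

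**Relative size.** The protocol window runs from Day 1 to Day L + 30. A 14-day shift is 14/210 = 6.7% of it if the last dose is on Day 180, 14/395 = 3.5% on Day 365, and 14/1491 = 0.9% on Day 1461. The shift matters less the longer the follow-up.

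**By-year denominators.** A subject is in a year's denominator if Treatment Period End Day falls in or after that year. Year 1 ends on Day 365 (SAP 6.4.9). With C − L = +14, a subject is added to the Year 2 denominator only if L + 30 ≤ 365 and L + 44 ≥ 366, so only if the last dose falls on Days 322 to 335. Any other last-dose day leaves the Year 2 denominator unchanged.

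**Interim.** In the 2015 interim analysis, every ongoing subject takes the Cutoff Date of 30 September 2015. Only subjects who had already completed can be affected.

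**Exposure date.** RFENDTN is the earliest of L, C and, at the interim, the Cutoff Date. When C is on or after L, the final-analysis value is L, which agrees with the protocol.

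**The case against.** The strongest reply is that the SAP's window is a reasonable choice. Causality is judged on drug, device and procedure together (Protocol 12.1.1), SAP 6.4.1 ties its safety window to the tube for that reason, and a transferring subject keeps the tube. Protocol 13.0 leaves analysis detail to the SAP. A reader might infer that the SAP's window is simply wrong. The documents do not support that; they show two different windows. What remains is that the protocol sets a specific rule for these subjects and the SAP replaces it without saying so.

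Three further readings are tempting and do not hold.

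- **A large gap.** Drug is dispensed every 6 weeks ± 7 days, which might suggest up to 49 days of study drug in hand after the final visit. SAP 8.3.1 has subjects return used and unused cassettes at each clinic visit, and nothing provides for dispensing study drug for use after the final one. Nor do the documents say what date sites enter as completion. If they enter the last-dose date, the gap is zero.
- **A count of misclassified events.** No adverse-event rate is given. The standard incidence tables count a subject once per preferred term (SAP 9.11.1), so a shift of days changes a count only if the subject had no other such event in the window. Transferring subjects normally have no follow-up visit (Protocol Table 2), so capture late in the window may be incomplete.
- **LCIG exposure mis-stated as well.** RFENDTN departs from the protocol only if dosing is recorded after completion.

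The reply also identifies a cost. Moving the whole safety Treatment Period to the last dose, with its 1-day allowance for data other than adverse events, could push the final visit into Post-Treatment if that visit falls more than one day after the last dose. It is the only visit with scheduled clinical labs and ECG (SAP 8.5.2 and 8.5.4). That limits the fix.

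**Conclusion.** The point holds as a minor, undeclared inconsistency between protocol and SAP. For completers who transfer to commercial LCIG and have no later PEG-J removal recorded, the SAP's TEAE window ends C − L days away from the protocol's. If C is later, events starting more than 30 days after the last study dose, possibly on commercial product, enter the study TEAE tables. If C is earlier, events that meet the protocol's definition leave them.

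The size cannot be computed from the documents. It is zero when the dates coincide and is probably small, since unused drug is due back at clinic visits. Protocol 11.0 requires the final assessments before transfer but does not tie the last study dose to that visit, so the dates may differ. A count changes only if an event starts in the mismatched days, and a by-year denominator only if the shift crosses a year boundary. The conclusion rests on the definitions alone and not on any assumed gap or event rate.

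**What to change.** In SAP 6.4.1 and 8.5.1, add a rule for completers who transfer to commercial product. The TEAE window and its Treatment Period End Day are anchored on the DS date of the last study dose, on the completion date if that is missing, and on the Cutoff Date if earlier at the interim. State in the same place that final-visit labs, ECG, vital signs and other non-AE assessments stay in the Treatment Period. Because Protocol 13.3 also ends treatment at the last dose for endpoint values, record that choice in SAP 10.1. The device-complication and tube-replacement tables (SAP 8.5.5.1 and 8.5.5.2) use the same End Day formula, so say which end day applies to them.

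Alternatively, keep the completion-date rule, declare it with its reason in SAP 10.1, and report how many subjects and TEAEs change class under the protocol's rule.

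The cost is one extra derivation from a date already collected, and separate end dates for AE and non-AE safety data in these subjects.

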13.4 Alpha Level Tested

Not applicable.

13.5 Sample Size

This is an open-label extension study. All subjects in a country where LCIG is not commercially available will be eligible to enroll if they meet the study's inclusion criteria and exclusion criteria.

14.0 Investigator Obligations

The Investigator agrees to conduct the clinical study in compliance with this protocol after the approval of the protocol by the IEC/IRB in compliance with local regulatory

requirements. The Investigator and the Sponsor will sign the protocol to confirm this agreement.

14.1 Essential Documents

The Investigator is responsible for providing and maintaining essential study documents. Essential study documents are those documents that individually and collectively permit the evaluation of the conduct of the study and the quality of the data produced. These documents serve to demonstrate the compliance of the Investigator and the Sponsor (or an authorized representative) with the standards of GCPs and with all applicable national regulatory requirements.

Essential study documents will include regulatory documents as well as source documents which are original documents, data and records of clinical findings, observations and other activities in a clinical study necessary for the reconstruction and evaluation of the study. Source documents will include hospital records, clinical and office charts, laboratory notes, memoranda, subject diaries or evaluation checklists, pharmacy dispensing records, recorded data from automated instruments, copies or transcriptions certified after verification as being accurate copies, microfiches, photographic negatives, microfilm or magnetic media, x-rays, subject files and records kept at the pharmacy, at the laboratories and at medical/technical departments involved in the clinical study.

The Investigator agrees to allow direct access to all essential clinical study documents for the purpose of monitoring and/or auditing by the Sponsor (or an authorized representative) and inspection by the appropriate national and foreign regulatory authorities.

